### **7.3 Screening/Baseline**

After signing the informed consent form, the study participant proceeds through the screening/baseline phase. Ideally, the screening/baseline procedures will be completed in two visits, but they can be completed in fewer visits or more visits if necessary. Under certain circumstances a participant will be allowed to re-consent and repeat the screening/baseline procedures. Participants who meet study eligibility and complete screening/baseline as outlined above will be randomly assigned to one of four medication orders.

### **7.4 Active Treatment Phase**

As outlined in Figure 1, the active treatment phase is 7 weeks in duration. During this time, participants will receive all four medications and will be scheduled for one research visit per week. Participants will be instructed not to smoke during medication evaluation weeks, which are study weeks 1, 2, 4 and 7. During medication evaluation weeks (i.e., Weeks 1, 2, 4, and 7) the research visits will be scheduled to occur during day 6 or 7 of the week in order to maximize participant exposure to the medication/placebo prior to assessment. All assessments ideally will be completed after the participant has received his/her methadone dose and before the participant smokes a cigarette, with the exception of the baseline visit when participants will be allowed to smoke prior to completing the assessments.

### **7.5 Follow-up**

A follow-up visit will be completed during study week 8. The measures to be collected during this visit are delineated in Table 2.

### **7.6 Medication and Trial Discontinuation**

#### **7.6.1 Medication Discontinuation**

An investigator may discontinue a participant's medication if he or she deems it clinically appropriate or, at the discretion of the investigator, for any of the reasons listed below.

1. significant side effects that are likely to have been caused by the study medication
2. serious or unexpected AEs which would make further study medication dosing not in the participant's best interest
3. inability or unwillingness of the participant to comply with the study protocol
4. serious intercurrent illness

A participant may discontinue medication anytime s/he wishes. Participants who wish to discontinue from study medication early or to withdraw from the study will have their medication discontinued. Any participant who discontinues the study prematurely, regardless of the reason, will be requested to return for a study close-out visit at the first opportunity. Whenever a study participant stops coming to the clinic without notification, staff will make a concerted effort to contact the participant (or the designated contact person if the participant cannot be contacted) to assure that they have had no untoward effects from study participation.

Study participants withdrawn from the protocol secondary to a medical or psychiatric concern will be referred for appropriate treatment. Participants will be asked to sign a general consent for the release of information to the referred health care provider. Study staff may request transportation for emergency treatment of a participant if medically appropriate (e.g., for acutely psychotic or suicidal participants).

### **7.6.2 Stopping Guidelines**

1. Dosing must be stopped immediately if the study clinician believes that continued dosing of study medication will be detrimental to the participant's mental or physical health.
2. Dosing must be stopped immediately if a participant makes a suicide attempt anytime during study participation.
3. Dosing must be stopped immediately if a study participant becomes pregnant during study participation. The participant will be referred to medical care for the pregnancy.
4. A participant must have a risk assessment performed by a qualified mental health professional to determine whether it is safe to continue dosing if, on the C-SSRS, he or she endorses thoughts or plans to commit suicide, and also endorses some intent to act on such thoughts or plans.
5. The study participant should seek immediate medical care in the following situations and then consult the study clinician to determine if it is safe to continue dosing:
  - If he or she experiences agitation, hostility, depressed mood, or other abnormal changes in thinking or behavior;
  - If he or she develops suicidal ideation or exhibits any suicidal behavior;
  - If he or she experiences new or worsening cardiovascular symptoms;
  - If he or she has signs and symptoms of a myocardial infarction;
  - If he or she has signs and symptoms of a stroke;
  - If he or she develops a serious skin rash with mucosal lesions;
  - If he or she develops hives or angioedema;
  - If he or she experiences any other severe hypersensitivity syndrome.

Participants who stop dosing for any reason will be eligible to continue attending study visits if they choose to remain in the study. If the participant wishes to end study participation, a study close-out visit will be conducted at the first opportunity.

### **7.6.3 Trial Discontinuation**

The study sponsor has the right to discontinue the investigation at any time.

## **7.7 Participant Reimbursement**

Participants will be reimbursed for their transportation, inconvenience, and time. This reimbursement will be in the form of gift cards or a Greenphire prepaid debit card. It is recommended that participants receive a total of \$70 for completing screening/baseline. To encourage participants to return the Quit Bit to the study team, a \$30 incentive payment is included at the Week 8 Follow-up Visit. The reimbursement schedule for study visits is outlined in Table 3. Using the reimbursement schedule, a participant could be reimbursed a maximum of \$365.

**Table 3: Reimbursement schedule for research visits**

Visit	Total per Visit (\$)	Total # of Visits	Grand Totals (\$)
Screening/baseline			70
Randomization Day	30	1	30
Weekly study visits (1 and 5)	35	2	70
Weekly study visits (2-4; 6-7)	25	5	125
Week 8 Follow-up visit	40	1	40
Incentive for return of the Quit Bit (Week 8)	30	1	30
Total			\$365

## **8.0 STUDY MEDICATIONS**

### **8.1 Nicotine Nasal Spray**

Nicotrol®NS (Distributed by Pharmacia & Upjohn Co Division of Pfizer Inc, NY, NY 10017) will be utilized in the study.

### **8.2 Varenicline**

Varenicline tartrate (Distributed by Pfizer Labs Division of Pfizer Inc, NY, NY 10017) will be utilized in the study.

### **8.3 Placebo**

Placebos for the Nicotrol®NS and varenicline tartrate will be obtained in cooperation with Pfizer Inc.

### **8.4 Dispensing Study Medication**

Dispensing will be completed by qualified study staff. NNS or placebo will be dispensed to participants at randomization (time "0" in Table 2) so that the use of NNS/PNS can start upon waking on the first day of study week 1. NNS/PNS or varenicline/placebo will be dispensed at weekly clinic visits as outlined in Table 2.

## **8.5 Storage**

Study medication will be stored in compliance with state law and institutional policy and in conditions as indicated on the product label.

## **8.6 Record of Administration**

Drug-accountability records including perpetual inventory, will be maintained at all times.

## **8.7 Used/Unused Supplies**

Unused study medication will be returned to the pharmacy (or other appropriately qualified entity based on local/state regulations) and logged into a perpetual inventory of study drug returned. The study staff will accurately maintain study drug accountability records.

## **8.8 Side Effects of Nicotine Nasal Spray**

The most common side effects:

- nasal irritation
- nasal congestion, rhinorrhea and sneezing
- eye irritation, watery eyes
- throat irritation, coughing
- transient changes in sense of smell or taste
- facial flushing

➤ These side effects are most common during the first week of use and generally improve with continued use of the nicotine nasal spray.

➤ The spray can be an irritant if it comes in direct contact with any mucous membrane or skin surface.

Dependence potential:

- In clinical trials, feelings of dependency on the spray were reported by 32% of active spray users compared with 13% of placebo spray users.
- Following the recommended dosing guidelines should minimize the tendency to become dependent on nicotine nasal spray.
  - The dosing guidelines recommend no more than 5 doses/hour and no more than 40 doses/24 hours.
  - Nicotine nasal spray should not be used for longer than 6 months.

## **8.9 Side Effects of Varenicline**

For patients taking the recommended dose of varenicline:

The most common side effects:

• nausea

• insomnia

• abnormal or vivid dreams

• constipation

• flatulence

	

• vomiting

• headache

• dry mouth

• general malaise or fatigue

--	--

Uncommon or rare, but potentially serious side effects:

➤ Neuropsychiatric Symptoms
 

• changes in mood (depression, mania)

• psychosis

• hallucinations

• paranoia

• delusions

• homicidal ideation

• hostility

• agitation

• anxiety

• panic

• worsening of pre-existing psychiatric illness

• suicidal ideation

• suicide attempt

• completed suicide

 
➤ Skin reactions
 

• Stevens-Johnson Syndrome

• Erythema multiforme

	
➤ Cardiovascular Events
 

• Angina pectoris

• Nonfatal myocardial infarction

• Need for coronary revascularization procedure

• New diagnosis of peripheral vascular disease

• Need for procedure to treat peripheral vascular disease

 
➤ Hypersensitivity Reactions
 

• swelling of the face, mouth (tongue, lips, and gums)

• swelling of extremities

• swelling of the neck (throat and larynx)

• angioedema

--	---

## 8.10 Concomitant Medications

Any medication (including prescription, over-the-counter, herbal supplements and health store products) to be taken during the study ideally should be approved by a study physician.

### Excluded Medications:

*These should not be taken for 30 days prior to study randomization and should not be used or prescribed for use during study participation:*

- Anticonvulsants
- Antiretroviral medications
- Biologics including human monoclonal antibody drugs such as HUMIRA
- Bupropion
- Insulin
- Naltrexone
- Nortriptyline
- Theophylline
- Warfarin
- Stimulants and appetite suppressants, either prescribed or over-the-counter, including Kava Kava and St. John's Wort
- Electroconvulsive therapy (ECT)
- Nicotine replacement therapy and other aids to smoking cessation which are not dispensed as study medication

### Episodic Use Permitted

*Please discuss with study physician if these are used within 30 days prior to screening visit:*

- Oral and injectable steroids are permitted on a short-term basis only

### **Chronic Use Permitted**

*These can be used without restrictions:*

- Acetaminophen
- Antidepressant medications, other than bupropion or nortriptyline
- Antihistamines
- Antihypertensive agents
- Aspirin
- Benzodiazepines (non-benzodiazepine hypnotics are also allowed)
- Bronchodilators
- COX-2 selective and non-selective medications, including NSAIDs
- Hormone Replacement Therapy
- Inhaled steroids
- Lipid-lowering agents
- Multivitamins
- Oral and depot contraceptives
- Oral diabetes medications
- Thyroid replacement
- Concomitant psychotherapy, phototherapy or light therapies

### **8.11 Treatment Plan**

Table 4 delineates the dosing schedule and the weeks during which medication efficacy will be evaluated. All participants will use NNS/PNS during days 1-7 of study weeks 1 and 2 and will be instructed to utilize the spray and to not smoke during those weeks. Participants will be taught how to deliver a 0.5 mg spray in each nostril and will be instructed that they may use the spray up to 40 times a day but no more than 5 times an hour. Participants will undergo dose escalation of varenicline/placebo during study weeks 3 and 6, and will be on full dose during weeks 4 and 7. Participants who are unable to tolerate the target dose (2 mg/day) will be titrated to the highest dose tolerated. Participants will be instructed to not smoke during weeks 4 and 7, which are the weeks during which the efficacy of varenicline/placebo will be assessed. It should be noted that participants assigned to a medication order in which varenicline is given before varenicline placebo (i.e., orders 1 and 3 in Table 1), will have a two-week washout period before placebo is tested - the first week is the official "wash out" week during week 5 and the second is week 6 during which the participant is undergoing dose escalation for placebo.

**Table 4: Schedule of medication dosing and evaluation of medication effect**

Week	Day	Medication/Placebo	Dose	Evaluation of Medication Effect
1	1-7	NNS/PNS	1 mg/dose up to 40x/day	Week 1
2	1-7	NNS/PNS	1 mg/dose up to 40x/day	Week 2
3	1-3	Varenicline/Placebo Dose Escalation	0.5 mg once daily	
	4-7		0.5 mg twice daily	
4	1-7	Varenicline/Placebo	1 mg twice daily	Week 4

5		Wash out		
6	1-3	Varenicline/Placebo	0.5 mg once daily	
	4-7	Dose Escalation	0.5 mg twice daily	
7	1-7	Varenicline/Placebo	1 mg twice daily	Week 7

Note: PNS=Placebo Nasal Spray; NNS=Nicotine Nasal Spray

## 9.0 ANALYTICAL PLAN

### 9.1 Primary Hypothesis

This study will test the hypothesis that, in M-M patients who experience elevated smoking during the 4-hour post-methadone-dosing period, both NNS and varenicline, relative to placebos, will reduce smoking during the post-methadone-dosing period.

### 9.2 Analysis Plan

All analyses will be completed using SAS, Version 9.3 (SAS Institute, 2010).

1. Primary outcome analysis. The primary outcome analysis will consist of two sets of statistical analyses, one comparing the effect of NNS to PNS on the proportion of daily cigarettes smoked during the 4-hour post-methadone-dosing period and one comparing the effect of varenicline to placebo on the proportion of daily cigarettes smoked during the 4-hour post-methadone-dosing period. The statistical approach taken to both sets of analyses will be the same. A normal mixed model regression will include treatment (active vs. placebo) and the proportion of cigarettes smoked during the post-methadone-dosing period during baseline as covariates. In addition, corrected Akaike Information Criterion (AICC), will be used to determine whether treatment order (see Table 1), time (days 1-7), and / or the treatment-by-time interaction should be included as covariates in the mixed model regression. The dependent variable will be the proportion of daily cigarettes smoked during the 4-hour post-methadone-dosing period from the weeks during which the medication/placebo is being evaluated (see Table 2). The baseline urine drug screen result (positive or negative for substances other than opioids) will be controlled for in the analyses.

2. Secondary outcome analyses. The present trial has six secondary objectives, the analytic approach taken for each is described below. The baseline urine drug screen result (positive or negative for substances other than opioids) will be controlled for in the analyses.

2a. Preliminary evaluation of the ability of the NNS and varenicline, relative to placebos, to reduce total cigarettes per day (CPD). This secondary outcome analysis will consist of two sets of statistical analyses, one comparing the effect of NNS to PNS on CPD and one comparing the effect of varenicline to placebo on CPD. The analytic approach utilized for the primary outcome analysis will be used for this analysis with the variable of interest being CPD (i.e., as opposed to the proportion of daily cigarettes smoked during the post-methadone-dosing period).

2b. Assessing the abuse liability of, and subjective feelings of dependence on, the NNS. The effect of NNS, compared to PNS, on the liability scale will be assessed using the same analysis procedure used for the primary outcome. The effect of treatment on the four-point dependence measure will be assessed with the same analysis procedure except that instead of a normal mixed model regression, a proportional odds logistic mixed model regression will be used.

2c. Exploratory analysis of the comparative efficacy of the NNS and varenicline in reducing cigarette smoking during the 4-hours post-methadone dosing period. The effect of NNS, compared to varenicline, on the proportion of daily cigarettes smoked during the 4-hour post-methadone-dosing period will be assessed using the same analysis procedure used for the primary outcome except that instead of comparing each experimental treatment to its respective placebo, the experimental treatments will be compared to each other. Because the order of NNS and varenicline is not counterbalanced (i.e., NNS is always received prior to varenicline), any significant differences may be due to an order effect and, thus, this is considered an exploratory analysis only.

2d. Exploratory analysis of the comparative efficacy of the NNS and varenicline in reducing total daily smoking in M-M patients. The analytic approach described in 2c will be used for this analysis with the variable of interest being CPD.

2e. Preliminary evaluation of the ability of the NNS and varenicline, relative to placebos, to decrease opioid and nicotine withdrawal. The analytic approach utilized for the primary outcome analysis will be used for these analyses with the variables of interest being SOWS total score and MNWS total score.

2f. Preliminary evaluation of the impact of the NNS and varenicline, relative to placebos, on the subjective experience of methadone. The analytic approach utilized for the primary outcome analysis will be used for these analyses with the variables of interest being each of the 5 items on the DEQ.

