## **6.0 STUDY DESIGN**

### **6.1 Overview of Study Design**

This is a 7-week, randomized-controlled crossover study with a follow-up visit at week 8. The portion of the study evaluating NNS and its placebo will be only single-blind, because of the inability to source an adequate matching placebo for the nicotine nasal spray. The portion of the study evaluating varenicline and

its matching placebo will be double-blind. Eligible participants will be randomized to receive the four interventions in one of four orders, with 5 patients assigned to each order; this design will serve to mitigate potential order effects. It should be noted that the study design is not fully counterbalanced in that varenicline and its placebo will always follow the NNS and its placebo. While it would be ideal to have a fully counterbalanced design, utilizing such a design would require an 11-week study, due to the dose escalation and washout periods required for varenicline/varenicline placebo. Given that the lack of a fully counterbalanced design impacts only the comparison of NNS and varenicline, which is a secondary objective/analysis, the decision was made to use the more efficient 7-week design.

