## **6.6 Randomization Plan**

Eligible participants will be randomized to receive the four interventions in one of four orders as outlined in Table 1, with 5 patients assigned to each order; this design will serve to mitigate potential order effects.

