**Table 1. The four medication orders to which participants will be randomized**

	Week 1	Week 2	Week 3-4	Week 6-7
Order 1	PNS	NNS	Varenicline	Placebo
Order 2	PNS	NNS	Placebo	Varenicline
Order 3	NNS	PNS	Varenicline	Placebo
Order 4	NNS	PNS	Placebo	Varenicline

Note: PNS=Placebo Nasal Spray; NNS=Nicotine Nasal Spray

Allocation sequence generation: The list of treatment assignments will be randomly generated prior to study initiation, employing a permuted-block scheme to ensure an approximately equal number of participants in each treatment group at any time during recruitment. Random assignments will be generated using standard randomization procedures in SAS software, and the master list of assignments will be stored by a non-study

staff member, in a secure, locked location. The master list will be used to assemble treatment kits prior to study initiation.

Treatment assignment: When an eligible participant is ready to be randomized, the staff member will assign the participant the next available kit (e.g., the first randomized participant gets kit #01, the second randomized participant gets kit #02, etc.). The randomizing staff member will write the assigned kit number on the participant's randomization source document, and track all treatment assignments in a master log kept with the treatment kits.

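### Each active-versus-placebo comparison is a two-period crossover, but the model has no period term and no AICC candidate can replace one

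*Combined protocol and SAP*

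**What the plan says.** Table 1 (section 6.6) and Table 4 (section 8.11) place the spray and its placebo in weeks 1 and 2, and evaluate varenicline and its placebo in weeks 4 and 7. Within each pair, half the participants receive active first. Section 6.1 describes the allocation as "with 5 patients assigned to each order; this design will serve to mitigate potential order effects".

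Section 9.2, item 1, applies one approach to both comparisons: a normal mixed model with treatment and baseline proportion, controlling for the baseline urine drug screen. AICC is then used to "determine whether treatment order (see Table 1), time (days 1-7), and / or the treatment-by-time interaction should be included as covariates". No section names a period or study-week term, a treatment-by-order interaction, or a covariance structure for the daily data.

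The model is reused. For cigarettes per day (2a), "The analytic approach utilized for the primary outcome analysis will be used for this analysis with the variable of interest being CPD". For abuse liability (2b), the effect "on the liability scale will be assessed using the same analysis procedure used for the primary outcome". Items 2e (withdrawal scales) and 2f (methadone drug-effect items) do the same.

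**The concern.** In a two-period crossover, each within-participant difference is the treatment effect plus or minus the period change, with the sign set by sequence. Counterbalancing cancels the period change in the average when the sequences are equal and complete. It does not remove it from the spread of the differences; only a model term does that. When the sequences are unequal, the cancellation fails as well.

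The plan accepts that order effects are possible but handles them by allocation alone. A change from week 1 to week 2 is most plausible for cigarettes per day and withdrawal. Section 7.4 says "Participants will be instructed not to smoke during medication evaluation weeks, which are study weeks 1, 2, 4 and 7", so week 2 follows a week of attempted abstinence and week 1 does not. For the primary proportion the documents give no evidence of drift, and a reduction spread evenly over the day would cancel in the ratio.

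At stake are power in a trial planned at only 78% and, if completion differs by sequence, a shift in the estimate.

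**Working it through.** **Can any listed term act as period?** A design matrix for one comparison (four orders, two weeks, seven days) was built with treatment, order, day, treatment-by-day and participant effects. Adding period raises its rank from 21 to 22, and the existing terms explain 0% of period (R-squared 0). Only treatment-by-order would reproduce period (R-squared 1), and it is not a candidate.

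**Reproducing the plan's power (section 9.3).** Inputs: SD .27, within-subject correlation .80, difference .11, n = 20, two-sided alpha .05.

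- SD of the paired difference = .27 × √(2 × (1 − .80)) = .1708
- Paired t-test, noncentral t, 19 df: 78.0%, which matches the stated 78%
- With period fitted, 18 df: 77.8%

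**Period omitted, sequences 10 versus 10.** The differences have mean τ + π in one sequence and τ − π in the other. The expected sample variance is .1708² + π² × n/(n − 1). At π = .10 this is .02916 + .01053 = .03969, an SD of .199 in place of .171. Simulation of week-level means (200,000 runs per setting, τ = .11) gives:

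| Assumed period change π | Power, omitted | Power, fitted | Test size, omitted |
|---|---|---|---|
| .02 | 77.6% | 78% | 4.8% |
| .03 | 77.0% | 78% | 4.7% |
| .05 | 75% | 78% | 4.2% |
| .10 | 67% | 78% | 2.4% |
| .15 | 53% | 78% | 1.0% |

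**Daily data.** These runs use seven values per week, with the weekly-mean variance and correlation held at the plan's values.

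- Participant and participant-by-week intercepts, day-to-day SD .10 to .25: the same 75/67/53% at π = .05/.10/.15.
- Participant intercept only: the loss is 0-2 points. The largest is 81.9% to 80.3%, at day SD .319 (the largest value compatible with the plan's figures) and π = .15.
- One simulated 20-participant data set (day SD .20, π = .10, both intercepts): treatment SE .0574 with treatment alone, still .0574 after adding order, day or both, and .0472 after adding period. The estimate did not change.

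**Unequal completion.** Section 9.3 considers 18 completers but gives no split by sequence. With two random dropouts from 20 there are 190 possible pairs.

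- Both fall in the same half of a given comparison in 2 × 45 = 90 pairs, so a 10 versus 8 split has probability 90/190 = 47%.
- If both participants are lost to both comparisons, at least one comparison is split in 140/190 = 74%. Only the 2 × 25 = 50 pairs that differ in both halves escape.
- Shift in the estimate at 10 versus 8 = π × 2/18, or .003, .006, .011 and .017 at π = .03, .05, .10 and .15.
- At τ = .12 and π = .10, power with period omitted is 60% or 78% depending on the direction of the change, against 79% with period fitted. Test size with period omitted is 1.5-4.8% over the range examined.

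**The case against.** The omission itself is hard to dispute, but its importance for the primary outcome can be.

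- **The harm is hypothetical.** The 67% and 53% figures need a period change about as large as, or larger than, the .11 treatment effect, and nothing in the documents supports that. At .03 or less the loss is about 1 point or less. This stands, which is why every figure here is conditional.
- **The SD is conservative.** Section 9.3 doubles a reported 2-hour SD of .135. At an assumed SD of .19, power is 97% with period fitted, and about 96% and 90% with it omitted at changes of .05 and .10. This stands as a sensitivity check; the true 4-hour SD is unknown.
- **The abstinence argument does not reach varenicline.** Weeks 4 and 7 each follow a dose-escalation week that is not an evaluation week. This stands: the stated mechanism applies to weeks 1 and 2 only.
- **The 74% needs both dropouts lost to both comparisons.** If both leave after week 2, the spray comparison stays 10 versus 10 and the chance is 47%, for varenicline alone. This also stands.
- **The participant-by-week intercept is a separate request with its own cost.** If its variance is truly zero, power is 76% against 82% for the simpler model. That advantage is real only in the zero-variance case. Where week-level variance exists, the participant-intercept-only model is anticonservative: its test size rises from about 5-6% at day SD .319 to 43% at day SD .10.
- **This is a pilot with counterbalanced pairs.** An omission that is unbiased under balance and conservative at week level does not create a false efficacy claim. This is correct and limits the severity.

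**Conclusion.** The concern holds. No fixed or candidate term in section 9.2 can separate week 1 from week 2 or week 4 from week 7. With complete 10 versus 10 sequences the estimate is unbiased, and on week-level data the test is conservative.

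The size of the loss depends on a period effect that the documents do not give. It is under about 1 point for changes of .03 or less, about 3 points at .05 and 11 points at .10, using the plan's SD and correlation and week-level error. Because the covariance structure is not stated, the loss for the daily primary outcome lies between these values and the 0-2 points of a participant-intercept model. The once-weekly outcomes in 2b, 2e and 2f are already week-level, so they have no daily values to dilute the loss. Cigarettes per day and withdrawal in weeks 1 and 2 are where a change is most plausible.

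This should be corrected but is not fatal. Confidence is high in the omission and lower in the size of its effect.

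**What to change.** Amend section 9.2, item 1, to state:

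> Each active-versus-placebo model will include treatment, period (week 1 vs 2 for the spray; week 4 vs 7 for varenicline), baseline value and baseline urine drug screen as fixed effects. Period is not subject to AICC selection. For daily outcomes the model will have random intercepts for participant and participant-by-week, with Kenward-Roger denominator degrees of freedom.

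Apply the period term to 2a, 2b, 2e and 2f; once-weekly outcomes need only the participant intercept. No change is asked in 2c and 2d, where treatment and study block cannot be separated, as the plan already acknowledges. Prespecify the term now, because adding it after seeing the data would be a post hoc choice.

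The change is to SAP wording only. Period costs one degree of freedom per comparison. If there is no period effect, power goes from 78.0% to 77.8% with 20 completers, and from 80.2% to 79.4% at 10 versus 8 with a difference of .12. The participant-by-week intercept costs nothing against the plan's 78%, which is already a week-level paired calculation, or up to about 2 points (76%) if its true variance is zero.
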